## **Patients and methods**

### **1. Study design**

A prospective study

### **2. Study setting**

The study will be conducted at Tygerberg Children's Hospital, Parow Valley, Cape Town. The hospital is the tertiary academic hospital of the Faculty of Medicine and Health Sciences, University of Stellenbosch. Children with tuberculous meningitis are referred from primary care day hospitals, district and secondary level hospitals from our drainage area. Children with suspected TBM are referred to our institution to establish the diagnosis of TBM and to treat the complications associated with advanced disease (stage 2 and 3 TBM, e.g. hydrocephalus). Research samples collected for the purposes of the current study shall be processed at the Stellenbosch University Immunology Research Group (SUN-IRG) laboratory, Department of Biomedical Sciences, Faculty of Medicine and Health Sciences. The SUN-IRG laboratory is accredited by the South African National Accreditation Agency as a specialist Immunology Research laboratory.

### **3. Inclusion and exclusion criteria:**

All children between the ages of 3 months and 13 years with suspected meningitis, and who require CSF examination for routine diagnostic purposes at Tygerberg Children's Hospital, where written consent is obtained will be included. If possible, assent will be obtained in those children older than 7 years who have a normal level of consciousness, i.e. a Glasgow Coma Score (GCS) of 15/15. Children 13 years and older will be excluded from the study. Failure to obtain written consent will also exclude children from the study.

The anticipated study period is November 2016 to December 2025. The estimated sample size, using a two-sample comparison of proportions (STATA®-Statistics/Data Analysis), required for each of the diagnostic aims of the study includes, at least, 72 children with definite or probable TBM and a total sample size of up to 460 patients (This includes children with TBM, bacterial

meningitis, viral meningitis and normal CSF). An average of 40 new TBM cases is admitted to our wards annually.

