## **Aims**

The main aims of the proposed project are as follows:

- 1) To validate a previously identified and patented three-marker CSF biosignature (IL-13, VEGF, cathelicidin LL37) for the diagnosis of TBM, in a new cohort of children with suspected TBM
- 2) To evaluate the usefulness of a recently identified and patented adult seven-marker serum protein biosignature (CRP, serum amyloid A, apolipoprotein A-1, transthyretin, complement factor H, interferon-gamma and IP-10) and other recently identified host markers, as a tool for the diagnosis of TBM
- 3) To investigate the usefulness of whole blood RNA transcripts as biosignatures for the diagnosis of TBM
- 4) To characterize the site of disease (CSF) versus peripheral blood immune profile of children with TBM, the response of immune cells to stimulation with *M.tb* antigens and explore differences between such responses in children with and those without TBM as part of student projects.
- 5) To develop a prototype point-of-care test based on host inflammatory protein biomarkers for

the rapid diagnosis of TBM (e.g. at the bedside) in children suspected of having TBM.

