### **Statistical methods and analysis plan**

Differences in the concentrations of individual host biomarkers between participants with TBM disease and those without TBM shall be evaluated by the Mann–Whitney U-test for non-parametric data analysis or the students t test, if data is normally distributed. P-values shall be deemed significant if less than 5%. The diagnostic accuracy of individual host biomarkers shall be investigated by receiver operator characteristics (ROC) curve analysis. The predictive abilities of combinations of analytes (biosignatures) shall be investigated by General discriminant analysis (GDA), random forests, and other biomarker analysis techniques, following the training/test set approach as done in previous studies . For Flow cytometry data, cell gating and data analysis will first be carried out on FlowJo software (Oregon, USA), followed by parametric (t-test) or non-parametric (Mann-Whitney U-) tests to assess the differences in quantities of immune cell

subpopulations, intra and extracellular cytokines and other biomarkers among children with TBM and those with other meningitis. Kruskall-Wallies test or one-way ANOVA with post-hoc analysis will be performed for comparison of more than 2 groups as advised by bioinformaticians from the Division of Molecular Biology and Human Genetics.

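### The analysis section does not exempt the existing signatures of aims 1 and 2 from refitting and a training/test split; locking them and testing them in all evaluable children keeps aim 1 an external validation and uses the whole cohort.

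*Combined protocol and SAP*

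**What the plan says.** - **Aims.** Aim 1 reads "To validate a previously identified and patented three-marker CSF biosignature (IL-13, VEGF, cathelicidin LL37) for the diagnosis of TBM, in a new cohort"; the children in it are suspected cases. Aim 2 begins "To evaluate the usefulness of a recently identified and patented adult seven-marker serum protein biosignature" and adds other recently identified markers. Both signatures therefore exist before this cohort is analysed.
- **Sample size (section 3, Inclusion and exclusion criteria).** The number "required for each of the diagnostic aims of the study includes, at least, 72 children with definite or probable TBM", within "a total sample size of up to 460 patients". No training or test set is mentioned there.
- **Accrual (same section).** On duration, the plan says: "The anticipated study period is November 2016 to December 2025". On the supply of cases, it says: "An average of 40 new TBM cases is admitted to our wards annually".
- **Analysis (Statistical methods and analysis plan).** Combinations of analytes are to be studied by "General discriminant analysis (GDA), random forests, and other biomarker analysis techniques, following the training/test set approach as done in previous studies". The section gives no split share, mentions no fixed coefficients or cut-offs, and has no separate rule for signatures that already exist.
- **Single markers (same section).** "The diagnostic accuracy of individual host biomarkers shall be investigated by receiver operator characteristics (ROC) curve analysis". This sentence carries no split, so the single-marker analyses are not affected.
- **Context.** The literature review (Use of host biomarkers in the diagnosis of TBM) reports 52% sensitivity and 95% specificity for the three-marker signature and says that this study will validate its accuracy. The sample-collection section distinguishes earlier pilot studies from the present validation study.

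**The concern.** A signature whose markers, weights and cut-off are fixed needs no training data in the cohort that tests it. Every new child with a usable result can count towards its accuracy. The only analysis text that covers signatures does not say this. It prescribes methods that estimate a model from data and then split the children.

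Two things are at stake for aims 1 and 2. First, a discriminant function re-estimated on the same three markers in the new children is a new model, and its test-set accuracy does not validate the existing one. Second, only the test fraction of the cohort would contribute to the estimate, which makes it less precise for no gain.

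This matters most for aim 1. The ethics section says that biomarkers validated here will go into the prototype bedside test, although the plan gives no numerical rule for that step.

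**Working it through.** **The plan's own figure.** The 72 cannot be reproduced. Section 3 names a two-sample comparison of proportions but gives neither proportion, nor the power, nor the allocation ratio. Many unrelated inputs give about 72. For example, 0.52 against 0.72 at 90% power, two-sided, with allocation 388:72, gives 71 cases and 454 children in total. On a 5-point grid of proportions at that ratio, 18 combinations land near 72. No match identifies the design, so the check below concerns precision and not power.

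**Inputs from the documents.** At least 72 TBM cases; up to 460 children; pilot sensitivity 0.52 and specificity 0.95; 40 TBM admissions a year; November 2016 to December 2025; five years of funding.

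**Assumption.** The test share is 20%, 30% or 50%. The documents state none.

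**Step 1: relative loss of precision.** The width of a confidence interval for a proportion is proportional to 1/√n. Testing on a share s of the children multiplies it by 1/√s, whatever the enrolment:
- s = 0.5: 1/√0.5 = 1.41
- s = 0.3: 1/√0.3 = 1.83
- s = 0.2: 1/√0.2 = 2.24

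**Step 2: intervals at 52% sensitivity.** These are Wilson 95% intervals, with centre (p + z²/2n)/(1 + z²/n) and half-width z√(p(1−p)/n + z²/4n²)/(1 + z²/n), for p = 0.52 and z = 1.96. For n = 72 the centre is 0.519 and the half-width 0.112, giving 40.7-63.1%.

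| TBM cases enrolled | Locked, all used | Test share | Cases tested | 95% CI |
|---|---|---|---|---|
| 72 | 40.7-63.1% | 50% | 36 | 36.3-67.3% |
| 72 | 40.7-63.1% | 30% | 22 | 32.4-71.0% |
| 72 | 40.7-63.1% | 20% | 14 | 28.4-74.8% |
| 200 | 45.1-58.8% | 30% | 60 | 39.6-64.1% |
| 367 | 46.9-57.1% | 30% | 110 | 42.8-61.1% |

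Wilson intervals widen slightly less than 1/√s when n is small. From 72 to 22 cases the width goes from 22.4 to 38.6 points, a factor of 1.72 rather than 1.83.

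**Step 3: specificity.** If 72 of 460 children have TBM, 460 − 72 = 388 do not. At 0.95 the simple half-width 1.96√(0.95 × 0.05/n) is 2.2 points with 388 children and 4.0 points with a 30% test set of 116. The loss falls mainly on sensitivity.

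**Step 4: does the tested number fall below 72?** A test set holds 72 cases once 72/s are enrolled: 72/0.5 = 144, 72/0.3 = 240 or 72/0.2 = 360. Forty admissions a year gives 5 × 40 = 200 over the funded period and 110/12 × 40 ≈ 367 over the whole study period, both before consent losses. So a 50% test set could reach 72 within the funded years. A 30% test set could do so only over the longer period, and a 20% test set only with almost every admission enrolled.

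**The case against.** The strongest reply is that aim 1 already implies the right analysis. The aims, the literature review and the sample-collection section together present the pilot as the source of the signature and the new children as its test. On that reading the split applies only to the search for new combinations. The approach is also specified by reference to earlier studies, which may define it. This stands in part: it is a reasonable account of what the sponsor intends. But the analysis section does not say it, and its wording covers signatures in general. A validation should not leave the choice open until the data are seen.

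A reader might infer more than this, and the documents do not support it:

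- **That the study is too small.** The 72 is a minimum, stated beside the total for all children, and reads most naturally as a cohort figure. At 40 admissions a year it is passed in under two years. With 200 cases, even a 30% test set gives 40-64%, almost the same as 72 cases unsplit.
- **That 72 must be the test set and cannot fit within 460.** This takes the less natural reading and needs a case mix that the plan does not give.
- **That power falls to some stated level.** The plan names no alternative sensitivity, so any power figure would rest on a hypothesis supplied from outside.
- **That the hold-out set should be dropped for new signatures.** Cross-validation uses the data more efficiently but gives up a separate test set. That is a trade-off and not an error in the plan.

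It is also fair to say that refitting the adult signature in children is a legitimate analysis under aim 2. It needs to be labelled as a new model.

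**Conclusion.** The point holds as a gap in the analysis section, not as a demonstrated sample-size defect. Read literally, the plan refits and splits signatures that could be tested as they stand. Aim 1 would then lose its status as an external validation of the existing signature, and the accuracy estimates for both existing signatures would have intervals about 1.4 to 2.2 times as wide as necessary.

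The relative loss holds at any enrolment but rests on an assumed 20-50% test share. The absolute intervals also rest on the pilot's 52% sensitivity and on the number enrolled. Whether fewer than 72 TBM cases would be tested cannot be settled from the documents. If the sponsor already means the pilot to be the training set, the change only makes that explicit. It should still be made before the new data are analysed.

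**What to change.** In the Statistical methods and analysis plan:

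1. State that the existing three-marker and seven-marker signatures will be applied with markers, coefficients and cut-offs fixed before the new data are analysed, and record those values.
2. Evaluate them in all children with a valid CSF or serum result and a reference classification, with no training set drawn from this cohort. Report sensitivity and specificity with 95% confidence intervals, and report this result first.
3. Treat any refit, for example of the adult signature in children, as a new signature and label it so.
4. Limit the training/test split to new signatures.

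This needs no extra children, samples or assays. The limitation is practical: the documents do not give the existing coefficients and cut-offs, and these must be usable on a comparable assay. If they are not, the refitted model must be reported as a new model and not as a validation.

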#### **4. Diagnostic work-up**

All patients will undergo a comprehensive clinical evaluation (Addendum1). Routine special investigations will be performed. CT of the brain will be done in all probable TBM cases and in other cases of meningitis when indicated. Air- encephalography will be performed in all TBM cases with hydrocephalus. MR imaging will be done as clinically indicated. Lumbar puncture will be performed and the following CSF investigations performed: appearance and colour determination; differential cell count determination by standard methods; protein, glucose and chloride determination by standard methods; centrifugation with Gram stain and India ink examination of the deposit; culture of the centrifuged deposit on blood agar plates for pyogenic bacteria; Auramine “O” staining & fluorescence microscopy, culture using the BBL™MGIT(Mycobacterium Growth Indicator Tubes)™ of Becton and Dickinson and detection of *Mtb* DNA using the HAIN Genotype MTBDRplus kit. Samples will be tested using Xpert Ultra and newer technologies e.g. AlereQ TB and the Savannah MTB assay. Microbiomic analysis will be performed on microbial DNA extracted from patient specimens and sequenced on the Illumina MiSeq platform. All data will be recorded on a pre-designed clinical data capture sheet (see addendum) and entered into a computerized database. Finally, data analysis will be carried out using appropriate software and statistical packages.

#### **The diagnosis of TBM will be made based on the following criteria:**

A diagnosis of **probable** TBM will be made if two or more of the following criteria are present in the setting of a characteristic history and CSF changes associated with TBM: A positive history of contact with an adult TB case, a positive tuberculin skin test, a chest x-ray suggestive of pulmonary tuberculosis (hilar lymphadenopathy, miliary tuberculosis or cavitation, CT or MRI demonstrating the characteristic features of TBM (ventricular dilatation, meningo-vascular enhancement and/or granuloma/s), poor weight gain or weight crossing percentiles documented on the Road to Health Card or positive identification of acid fast bacilli from gastric washings (microscopy or culture).

A diagnosis of **definite** TBM will be made if acid-fast bacilli is present in the CSF, *Mtb* is cultured

from CSF, a nucleic acid amplification test of CSF is positive or there is histopathological evidence of *Mtb* from another central nervous system site. The degree of TBM will be classified according to the proposed modified British Medical Research Council (BMRC) classification of 1948. -Stage I: Glasgow Coma Scale (GCS) of 15 and no focal neurology, Stage IIa: GCS of 15 plus focal neurology, Stage IIb: GCS of 11-14 with focal neurology, Stage III: GCS <11. All investigations required for establishing a diagnosis (TBM or no TBM) are usually done routinely and shall therefore not specifically be as part of the current study.

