**Literature review**

**Introduction**

Tuberculous meningitis (TBM) is the most common type of bacterial meningitis in the Western Cape Province (WCP) of South Africa . The tuberculosis (TB) incidence in South Africa has risen from 301 new cases/100,000 population in 1990 to 948 new cases/100,000 population in 2007 , and although the world-wide incidence of the disease has fallen by an average of 1.5% per year since 2000, the incidence of the disease in South Africa is still 834 per 100, 000 population as indicated by recent World Health Organization (WHO) reports . The TB burden is worsened by the human immunodeficiency virus (HIV) pandemic. TBM represents the most severe manifestation of TB with high morbidity and mortality, despite adequate anti-TB therapy. This is mainly the result of delayed diagnosis and initiation of appropriate therapy . The pathogenesis of TB is still poorly understood. Despite ongoing research, early, cost-effective diagnostic tools are lacking . Demonstration of acid-fast bacilli and/or culture of *Mycobacterium tuberculosis* (*Mtb*) from cerebrospinal fluid (CSF) represents the gold standard for diagnosing TBM, but unfortunately the sensitivity of both these tests is low . The sensitivity of the recently developed GeneXpert

test (Cepheid Inc., USA) for TBM is ~50-60%, but only improves to 72% when CSF is centrifuged as demonstrated in a recent study . The diagnosis of TBM is therefore based on a combination of clinical, laboratory and radiological findings. However, a clinical diagnosis is often delayed, especially in the early stages of the disease when few neurological signs may be present. In addition, the CSF picture can be highly variable . Although various case definitions for TBM have been reported in the literature, diagnostic criteria vary widely, so that no standardized case definition exists . An international workshop on TBM was held during May 2009 in Cape Town, South Africa. This was attended by international experts on TBM, and a uniform case definition for TBM was proposed for future research.

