### **Uniform research case definition for TBM **

It is proposed that patients suspected of having TBM be categorized into definite, probable, possible and no TBM. This is proposed to obtain standardization for research purposes, for adults and children, and was not primarily devised as a clinical tool. The clinical diagnosis of TBM (probable or possible) is based on clinical findings and special investigations (Table 1). The boundaries between groups are not fixed, and patients can interchange between groups, based on results of laboratory and radiological investigations. Definite TBM requires demonstration of acid-fast bacilli in the CSF, *Mycobacterium tuberculosis* culture from CSF, a positive nucleic acid amplification test (PCR) of CSF or histopathological evidence of *Mycobacterium tuberculosis* from a central nervous system site.

Patients must have a clinical diagnosis of meningitis including one or more of the following symptoms: headache, irritability, vomiting, fever and neck stiffness (Table 1). The diagnosis of probable or possible TBM is based on 1) clinical findings 2) CSF results 3) neuroimaging findings 4) evidence for TB outside the central nervous system and 5) additional laboratory criteria. A scoring system then determines whether a patient falls in the probable or possible TBM category (Table 1). Points are allocated for a positive finding in each of the categories, with a maximum score for each category. A total score of at least 10 is compatible with probable TBM, while a total score of at least 6 equates with a possible TBM diagnosis. A certain number of points have to come from the CSF or neuro-imaging criteria to ensure that the patient is indeed suffering from meningitis and not some other chronic type of tuberculosis. It is also suggested by the consensus

group that all patients should have additional CSF investigations to exclude alternative causes for the clinical presentation.

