In practice, a clinical case definition of bacterial meningitis is needed because most patients admitted to a tertiary setting such as Tygerberg Hospital, will already have had antibiotics, which usually results in negative blood and CSF cultures . Similarly, a definite or clinical diagnosis of viral meningitis as possible cause for aseptic meningitis is critical, since aseptic meningitis is frequently caused by viruses . If an alternative cause is found for the clinical presentation, a diagnosis of not-TBM should be made, excepting where dual infection is confirmed.

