## **Hypothesis**

CSF and blood samples obtained from children with TBM will possess distinct host biosignatures in comparison to CSF and blood samples from children with other forms of meningitis and these biosignatures can be used as a tool for the rapid diagnosis of TBM.

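### The TBM case definition has no alternative-cause exception and gives indeterminate children no place, so the reference label behind every accuracy estimate is incomplete

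*Combined protocol and SAP*

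**What the plan says.** The operative definition is in section 4 (Diagnostic work-up), under the heading on the diagnosis of TBM. Probable TBM is diagnosed when "two or more of the following criteria are present in the setting of a characteristic history and CSF changes associated with TBM". Definite TBM needs a positive CSF smear, culture or nucleic acid test, or histopathology from the central nervous system, and none of the listed criteria. No other category is defined. The same section remarks that "All investigations required for establishing a diagnosis (TBM or no TBM) are usually done routinely", without saying what no TBM means.

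The literature review (Uniform research case definition for TBM) describes four research categories: definite, probable, possible and no TBM. There, "a total score of at least 6 equates with a possible TBM diagnosis". It continues: "If an alternative cause is found for the clinical presentation, a diagnosis of not-TBM should be made, excepting where dual infection is confirmed". Section 4 adopts neither the possible category nor the alternative-cause rule.

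The comparison group is described in several ways:
- Section 3 enrols "All children between the ages of 3 months and 13 years with suspected meningitis" who need CSF examination and have written consent. It counts cases as definite or probable TBM and names bacterial meningitis, viral meningitis and normal CSF as the other groups.
- The Hypothesis sets TBM samples "in comparison to CSF and blood samples from children with other forms of meningitis".
- Statistical methods and analysis plan first compares children with and without TBM. For flow cytometry it compares TBM with other meningitis. Its ROC and biosignature sentences name no comparator.

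**The concern.** Sensitivity, specificity and area under the ROC curve for each biosignature are measured against this label, and combined signatures are both trained and tested on it.

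The protocol itself gives reason to expect children at the boundary. It says that CSF smear or culture "represents the gold standard for diagnosing TBM, but unfortunately the sensitivity of both these tests is low", that clinical diagnosis is often late, and that the CSF picture varies. Section 2 says that children with suspected TBM are referred to this hospital to have the diagnosis established. The literature review adds that most children reach a hospital of this kind after antibiotics, which usually makes cultures negative.

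If the handling of these children is settled only once biomarker results are known, it can be chosen to suit them. Aim 1 is to validate a patented signature, so that risk matters whatever the size of the bias.

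**Working it through.** **Inputs**
- Pilot three-marker CSF signature: sensitivity 52%, specificity 95%, predictive values 91% and 66% (literature review, host biomarkers).
- At least 72 definite or probable TBM, up to 460 in total (section 3).
- Sensitivity of GeneXpert "for TBM is ~50-60%, but only improves to 72% when CSF is centrifuged" (Introduction).
- Assumed, with no source in the documents: the number of cases with another cause, and the share of unproven TBM children who fail the two-criteria rule.

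**1. The plan's own figures.** The 72 and 460 can be neither confirmed nor refuted, because the two proportions, power and allocation are not stated. On a 5-point grid of proportions (two-sided 5%, power 80% or 90%), 19 input sets give about 72. Nothing below depends on how 72 was derived.

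The pilot figures agree with each other. The TBM share implied by the positive predictive value is 0.91×0.05 / (0.91×0.05 + 0.52×0.09) = 0.493. That gives a negative predictive value of 0.95×0.507 / (0.95×0.507 + 0.48×0.493) = 0.67, against 66% stated.

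**2. Where two kinds of child fall**
- *Child A: TB contact, poor weight gain, compatible history and CSF, and another proven cause.* Section 4 gives probable TBM. The literature review gives not-TBM unless dual infection is confirmed. Section 3's list would also admit the child as bacterial or viral meningitis, and no rule says which label wins.
- *Child B: compatible history and CSF, fewer than two criteria, no CSF or tissue proof.* Section 4 gives neither definite nor probable. The literature review's score could give possible TBM. The with-versus-without-TBM comparison makes the child a control. Section 3's list and the other-meningitis wording leave the child out: the CSF is not normal, and no bacterial or viral cause has been identified.

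**3. Child A and sensitivity.** Suppose c of 72 labelled cases have another cause and test positive at the false-positive rate of 5%:

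apparent sensitivity = [(72 − c)×0.52 + c×0.05] / 72

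The loss per child is 0.47/72 = 0.0065, or 0.65 points. With c = 3 (assumed), 36.03/72 = 50.0%.

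**4. Child B and specificity, control reading only.** Controls number at most 460 − 72 = 388. With t true TBM children among them:

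apparent specificity = [(388 − t)×0.95 + t×0.48] / 388

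The loss per child is 0.47/388 = 0.0012, or 0.12 points, so about 8 children cost one point. With t = 20, 359.2/388 = 92.6%. For a signature with an assumed sensitivity of 80%, t = 20 gives (368×0.95 + 20×0.20)/388 = 91.1%.

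For a rough scale of t, let u be the share of TBM without CSF proof and f the share of those who fail the two-criteria rule. The hidden cases beside 72 counted ones are h = 72uf/(1 − uf).
- u = 0.28 (1 − 0.72), f = 0.10: h = 2.1, specificity 94.7%.
- u = 0.40 (1 − 0.60), f = 0.25: h = 8.0, specificity 94.0%.
- u = 0.50 (1 − 0.50), f = 0.40: h = 18.0, specificity 92.8%.

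The u values use GeneXpert alone. Section 4 adds microscopy, culture, MTBDRplus and Xpert Ultra, so u should be lower.

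**5. Child B, drop-out reading.** Specificity is not lowered. Instead the hardest children leave the comparison, which can make accuracy look better than it would be among all children with suspected meningitis. The documents give no basis for a figure.

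**The case against.** A reader might infer that the plan turns every unproven TBM-like child into a control and so biases specificity down. The documents do not support that. The remark about TBM or no TBM is an aside about routine investigations, not a classification rule. Section 3's named groups, the Hypothesis and the flow cytometry sentence all fit a narrower comparator that leaves such a child out. This objection stands: control status is one reading, and the direction of bias depends on which reading is used.

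It can also be said that clinicians would not leave a TBM label on a child with another proven cause. The literature review says that children can move between groups as results arrive, section 4 includes Gram stain, India ink and pyogenic culture, and section 5 treats bacterial and viral meningitis as separate diagnoses. That makes sensible handling likely, but section 4 states its probable rule without an exception. The alternative-cause rule is background text, so this is a failure to carry it over, not a clash between two operative rules.

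The illustrated shifts are modest beside sampling error. The 95% half-widths are about 1.96×√(0.95×0.05/388) = 2.2 points for specificity and 1.96×√(0.52×0.48/72) = 11.5 points for sensitivity. That bears on urgency. It does not remove the gap, because misclassification bias does not shrink with sample size and an open choice of label remains open.

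Table 1, the addenda and the data capture sheet were not available and may hold a rule.

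**Conclusion.** The point holds in two parts of different strength. The missing alternative-cause exception follows directly from section 4 as written, and its effect is to lower apparent sensitivity, by 0.65 points per child among 72 cases at pilot accuracy. The place of the indeterminate child is unspecified: it may lower apparent specificity or flatter accuracy.

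No size can be derived from the documents. The specificity figures illustrate the control reading only and should not be read as estimates. They treat pilot accuracy as true, take the maximum of 388 controls and use assumed shares. The calculations also assume that mislabelled children test as their true disease state would predict. This should be fixed because the reference label underlies every diagnostic aim and the remedy is cheap.

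**What to change.** For research classification only, leaving clinical care unchanged:
1. In section 4, add the literature review's not-TBM rule with its dual-infection exception.
2. In section 4, add a possible or indeterminate category. Use the literature review's score if its items are recorded; otherwise a plain indeterminate group needs no score.
3. In Statistical methods and analysis plan, state the ROC and biosignature comparison as definite plus probable TBM against not-TBM. Report the indeterminate group separately. Beside the main result, give pre-stated analyses counting that group as TBM and as not-TBM, and one restricting cases to definite TBM.

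If Table 1, the addenda or the data sheet already contain such a rule, a cross-reference in section 4 and in the statistical section is enough.

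The cost is protocol wording, one extra category and a few analyses, with no new samples or tests. Whether the score items are recorded must be checked first. The drawback is that some children leave the main comparison, which can itself flatter accuracy, so the both-ways results must always appear with it.
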